4.3 JUSTIFICATION FOR DOSE

Phase 1/2 clinical study of Galnobax® established that Galnobax® is safe for long term use (tested for 12-weeks) in both 14% and 20% concentrations. The efficacy analysis showed that Galnobax® treatment has advantage in terms of area and volume reduction over Placebo. The advantage of Galnobax® 14% is even more pronounced in hard to heal wounds. Considering this fact, this study has been planned to investigate Galnobax® 14% in a phase 3 trial to establish safety and efficacy in a larger number of Subjects for statistical significance.

Each eligible Study Subject will be assigned to one of the three treatment groups as described in Table 2 and will receive the next available consecutive randomization number.

Table 2 Dosing schedule

Gr. No.	Study group	Treatment frequency
1	Standard of Care + Galnobax® gel	Twice daily
2	Standard of Care	Twice daily
3	Standard of Care + Vehicle gel	Twice daily

Dose Modification for Study Drug

If any adverse reaction potentially related to Study drug is observed in terms of hypersensitivity or local allergic reaction at or around the Target Ulcer site, Investigator may decide to discontinue the

study drug administration to the Subject or adjust the frequency per the requirement for a limited period.

4.4 END OF STUDY DEFINITION

A participant is considered to have completed the Study if he or she has completed all phases of the study including the last visit or the last scheduled procedure shown in the Schedule of Activities (SoA), [Section 1.3](#). The end of the study is defined as completion of the last visit or procedure shown in the SoA in the trial. In addition, if Subject is discontinued or withdrawn from the Study, the last recorded visit of such Subject shall be considered as the End of Study.

5 STUDY POPULATION

The Subjects included in this Phase 3 clinical study are those having DFU which has not healed for at least 6 weeks and satisfy eligibility criteria described below. It is made explicitly clear that there will be only one Target Ulcer per patient.

5.1 INCLUSION CRITERIA

The Subjects would be included in the Study if they satisfy all of the following inclusion criteria: Potential Subjects are required to meet all of the following criteria for enrollment into the Study and subsequent randomization:

1. Subjects, male or female, aged 18 to 75 years (inclusive) with Type 1 or Type 2 diabetes undergoing therapy for glycemic control
2. Subject has glycosylated hemoglobin, HbA1_C, ≤ 12%
3. Subject with diagnosis of neuropathic foot ulcer by 10g monofilament test
4. Subject has adequate vascular perfusion of the affected limb, confirmed by Ankle-Brachial Index (ABI) ≥ 0.65 and ≤ 1.3

Note: If the ABI measurement is >1.30 one of the following confirmatory tests must be performed for Subject to be considered eligible. Prior documented flow study within the last 3 months of the Screening Visit is acceptable

- a) Great Toe pressure (plethysmography) > 40 mm Hg;
- b) Transcutaneous partial pressure oxygen (TcPO₂) at the foot > 40 mm Hg;
- c) Skin Perfusion Pressure (SPP) > 40 mm Hg;
- d) Doppler ultrasound (biphasic or triphasic waveforms) consistent with adequate blood flow to the affected extremity, as determined by the standard practices of the Investigator and the site

5. Presence of at least one DFU that meets all of the following criteria:
 - a) A full-thickness ulcer of Grade A1 as per Texas classification system;
 - b) Ulcer is located below or up to 5 cm above the malleoli (excluding ulcers between the toes);
 - c) Ulcer size (area) is ≥ 2 cm² and ≤ 15 cm² (post-debridement);
 - d) There is a minimum 3 cm margin between the qualifying Target Ulcer and any other ulcers on the specified foot, post-debridement;
 - e) No exposed bone, tendon, muscle, ligament or joint capsule, and no tunneling, undermining, or sinus tracts;
 - f) Unresponsive to ulcer care and open for at least 6 weeks at the time of the Screening Visit;
 - g) Ulcer is non-infected as determined by clinical assessment and complete hemogram;

- h) Ulcer has a clean, granulating base free of adherent slough to the greatest extent possible as per Investigator;
- i) Ulcer area reduction < 30% from the Screening Visit to Baseline visit

Note: Criterion 4(i) will be evaluated at the time of randomization. If the Subject has more than one qualifying DFU, the ulcer designated as the Target Ulcer should be the ulcer preferably on the plantar region which is older, deeper and with a larger area.

- 6. Clinically normal resting 12-lead ECG at Screening Visit or, if abnormal, considered not clinically significant by the Investigator
- 7. Subject, if female of child-bearing potential, has a negative urine pregnancy test at Screening and willing to use acceptable methods of contraception (birth control pills, barriers) or abstinence throughout the Study
- 8. Subject is able and willing to comply with Study procedures including the use of an off-loading device (as applicable for the location of the ulcer) and adhere to protocol during the Study in the opinion of Investigator
- 9. A Subject or LAR agrees to sign informed consent form and allow audio visual recording of consent, if applicable

5.2 EXCLUSION CRITERIA

Subjects will not be eligible for enrolment in the Study if they meet any of the exclusion criteria listed below:

- 1. Actively infected ulcers with or without purulent discharge, ulcers with exposed bone or associated with osteomyelitis

Note: The osteomyelitis should be ruled out by clinical examination and X-ray findings where found necessary by the Investigator. If the Investigator is unable to ascertain the condition of osteomyelitis by probing of the Target Ulcer or digital X-ray then Investigator may use other techniques such as MRI, bone scintigraphy, leukocyte scanning or bone biopsy to rule out the presence of osteomyelitis based on availability of the investigation facility at the clinical sites.

Note: If foot has more than one ulcers and one of them is infected, then Target Ulcer should not be selected from this foot unless all ulcers on the foot are free of infection. If Subject has ulcers on both feet and infection is seen in the ulcer on non-target foot, Subject may be included in the Study with prescribing oral antibiotic treatment for non-Target Ulcer.

- 2. Subjects with more than three ulcers below knee
- 3. Subjects with Target Ulcer requiring off-loading that cannot be effectively off-loaded; or unable to tolerate the off-loading method
- 4. Subject has ulcers caused by a disease other than diabetes, e.g., fungal ulcerations, malignant ulcerations, and ulcerations due to venous or arterial insufficiency, or due to hematological disorders, in the opinion of the Investigator
- 5. Ulcer, about which the Investigator is suspicious for cancer

Note: In case of such suspicion, ulcer present more than 1 year will require a 3 mm punch biopsy to rule out malignancy. Prior documented negative ulcer biopsy within the last 1 year of the Screening Visit is acceptable

- 6. Subjects with a gangrenous or ischemic ulcer
- 7. Subject with ulcer that in the opinion of the Investigator, may need amputation
- 8. Subject with Target ulcer where wound measurement is not possible, such as ulcers between toes
- 9. Body mass index (BMI) > 40 kg/m²
- 10. Laboratory values at Screening of:
 - a) Hemoglobin < 10.0 g/dL

- b) White Blood Cells (WBC) $< 2.0 \times 10^9$ cells/L
- c) Liver function studies [Total bilirubin, aspartate aminotransferase (AST) and alanine transaminase (ALT)] $> 3x$ the upper limit of normal
- d) Albumin < 2.5 g/dL
- e) eGFR < 25 mL/min

11. Presence of any existing clinically significant medical condition(s) that, in the opinion of the Investigator, could interfere with wound healing, including but not limited to the following:

- a) Vasculitis or connective tissue disease
- b) Buerger's disease, Raynaud's or other peripheral vascular disease
- c) Clinically significant claudication or peripheral edema on the affected limb
- d) Acute or unstable Charcot foot
- e) Aplastic anemia or exacerbation of sickle cell anemia
- f) Current sepsis
- g) Congestive heart failure (NYHA Class III or IV), coronary heart disease with ST segment elevation, myocardial infarction, or coronary artery bypass graft or percutaneous transluminal coronary angioplasty within the last 6 months
- h) End-stage renal disease
- i) Immunosuppression
- j) Acquired immune deficiency syndrome (AIDS) or HIV positive
- k) Any malignancy history

12. Subject has received or is currently receiving or scheduled to receive any of following medication or therapies during the course of the Study

- a) Immunosuppressants (chronic systemic corticosteroids) within 30 days of randomization visit
- b) Revascularization surgery (e.g., angioplasty, coronary artery bypass surgery, transmyocardial revascularization) within 30 days of randomization visit
- c) Growth factors within 30 days of randomization visit
- d) Hyperbaric oxygen therapy (HBOT) within last 7 days of randomization visit
- e) Negative pressure wound therapy (NPWT) within last 7 days of randomization visit
- f) Bioengineered tissue or skin substitutes within 30 days of randomization visit
- g) Application of topical steroids to the ulcer surface within 30 days of randomization visit
- h) Use of any investigational drug(s) or therapies within 30 days of randomization visit

13. Subject with intolerance to β -blockers at any time in the past

14. Has any other factor which may, in the opinion of the Investigator, compromise participation and/or follow-up in the Study

5.3 LIFESTYLE CONSIDERATIONS

Not applicable

5.4 SCREEN FAILURES

Screen failures are defined as participants who consent to participate in the clinical trial but are not subsequently randomly assigned to the study intervention or entered in the study. This will occur to those Subject who did not meet the eligibility criteria at Baseline Visit or whose Target Ulcer reduces in area by $\geq 30\%$ during the Screening period. Such Subject is considered screen failed

and will exit from the Study without any further evaluation. Subject who has screen-failed once may be rescreened at an appropriate time as decided by the Investigator. Only one such rescreening is allowed for any Subject during the study.

5.5 STRATEGIES FOR RECRUITMENT AND RETENTION

The recruitment and retention strategies would be detailed in the clinical trial management plan (CTMP) and monitoring plan (MP) including the site-specific plans as per the site-specific standard operating procedure (SOP). The considerations for recruitment and retention strategies would include the following but not limited to:

- Target study sample size as consistent with information contained in **Sample Size Determination**
- Anticipated accrual rate
- Anticipated number of sites and participants to be enrolled for the study
- Source of participants
- Recruitment venues
- How potential participants will be identified and approached
- Types of recruitment strategies planned
- Procedures to enhance retention of patient in the study
- Participants compensation/incentives for the study

6 STUDY INTERVENTION

6.1 STUDY INTERVENTION(S) ADMINISTRATION

6.1.1 STUDY INTERVENTION DESCRIPTION

Test IP (Galnobax®)

Galnobax® is a topical gel containing 14% Esmolol hydrochloride. The gel will be packaged into lacquered aluminium tube in the quantity of 15 g per tube for both morning and evening application on the Target Ulcer. *The composition of the Galnobax® gel is as shown in Table 3*

Table 3 Composition of Galnobax®

INGREDIENTS
Active Ingredient
Esmolol hydrochloride
Inactive Ingredients
Benzalkonium chloride solution
Poloxamer 338
Sodium Acetate Trihydrate
Glacial Acetic Acid
Concentrated Hydrochloric Acid
Purified water

Vehicle gel

The Vehicle gel to match the IP will be supplied by the Sponsor. The Vehicle gel will be without active ingredient but will have all inactive ingredients in the same concentration as used in Galnobax® gel.

Standard of Care

The SoC includes wound cleaning by normal saline, maintenance of moist wound environment and off-loading of the Target Ulcer. In addition, during site visits removal of necrotic, infected and/or nonviable tissue by debridement and management of infection will be done by the Investigator, if required.

6.1.2 DOSING AND ADMINISTRATION

The amount of the IP (Galnobax®) or Vehicle gel to be applied will vary depending upon the area and depth of the Target Ulcer. To calculate the length of gel to apply to the Target Ulcer such that a uniform layer of IP over the wound surface, refer the Target Ulcer area obtained using advance camera in the corresponding visit and use the following formula to calculate the length of gel in centimeters to be applied:

Length of Gel in Centimeters to be applied at each application

= Area of ulcer in cm^2 (using advance camera) X 0.6 centimeter of gel from 15 g tube

For example, if the ulcer area measures 10 cm^2 , then a 6-centimeter length of gel should be used from a 15 g tube [$10 \times 0.6 = 6 \text{ cm}$].

Further, depending on the surface area of Target Ulcer, additional amount of IP may be applied to ensure formation of uniform layer of IP over the wound bed.

How to administer treatment (Instructions to unblinded Investigator and Study Nurse):

a. For group randomized to IP (Galnobax®)/Vehicle + SoC treatment

For morning application:

1. Remove the dressing
2. Rinse the Target Ulcer using saline
3. Squeeze out the required length of the gel from tube on to a sterile wax paper (printed with centimeter scale) provided with the kit
4. Using sterile applicator (provided with the kit) spread the gel over the entire ulcer area to yield a thin continuous layer that covers the wound bed, but no peri-wound skin
5. The Target Ulcer will then be covered by appropriate dressing and the Subject must be advised to leave it in place till next application

For evening application:

1. Remove the dressing
2. Only the peri ulcer area should be cleaned by cotton dipped in saline (do not rinse the Target Ulcer by saline for evening application)
3. Squeeze out the required length of the gel from tube on to a sterile wax paper (printed with centimeter scale) provided with the kit
4. Using sterile applicator (provided with the kit) spread the gel over the entire ulcer area to yield a thin continuous layer that covers the wound bed, but no peri-wound skin

5. The Target Ulcer will then be covered by appropriate dressing and the Subject must be advised to leave it in place till next application

b. For group randomized to SoC treatment

For morning application:

1. If the Target Ulcer is already dressed, remove the dressing
2. Rinse the Target Ulcer using saline
3. The Target Ulcer will then be covered by appropriate dressing and the Subject must be advised to leave it in place till next application.

For evening application:

1. The dressing should be removed
2. Only the peri ulcer area should be cleaned by cotton dipped in saline (do not rinse the Target Ulcer by saline for evening application)
3. The Target Ulcer will then be covered by appropriate dressing and the Subject must be advised to leave it in place till next application

6.2 PREPARATION/HANDLING/STORAGE/ACCOUNTABILITY

6.2.1 ACQUISITION AND ACCOUNTABILITY

The Sponsor/Contract Research Organization (CRO) will provide IP (Galnobax® as well as Vehicle gel) to the site. The accountability of IP will be maintained as follows:

- The Investigator/co-Investigators or designee would acknowledge receipt of Study IP supplies for each shipment received
- The unblinded Investigator responsible for dispensing the IP to the Study Nurse must maintain a drug accountability log. The IP accountability log records the receipt, dispensing and return of the IP
- At any time the sum of quantity of used and unused IP should match with the quantity of medication supplied. Account must be given of any discrepancies
- The Study monitor and Sponsor should be notified immediately of details of any IP, which is inadvertently damaged or lost
- The used or unused IP tubes will be returned by the Study Nurse to the site. Tubes will be replenished as required with identical kit number
- The quantity of IP utilized for the treatment will be monitored by checking the weight of the tube at the time of issuing it for the treatment and at the time of collecting the used tube
- If all tubes from the kit are consumed, a new kit with identical treatment will be issued

Handling of Investigational Product:

Both used and unused IP tubes would be sent back to Sponsor/their representative for destruction as per standard procedure. Reconciliation between the amount of IP supplied, used and returned to the Sponsor must be performed by the Sites and the CRO. If any discrepancies are found in the reconciliation of IP, it will be resolved. This reconciliation will be logged by each site on the IP reconciliation form, signed and dated.

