6.2.2 FORMULATION, APPEARANCE, PACKAGING, AND LABELING

Formulation and Appearance

The details of formulation are given in [Section 6.1.1](#). The IP is a colorless gel at room temperature.

Packaging

The IP will be packaged in to lacquered aluminium tubes in the quantity of 15 g per tube. The tubes will be placed in cartons which has product information and kit number printed on it (Table 4). Each carton will contain one tube. Each kit will contain 4 such cartons and two boxes of sterile gel measurement strips. Sufficient number of such kits will be made available to ensure sufficient supply of IP for the Study.

Table 4 Labelling information of Galnobax®

Galnobax® Topical Gel Study code: NG-A16		
Kit No.:		
Topical gel contains		Net Wt.
Vehicle or Esmolol Hydrochloride	14% w/w	15 g
Preservative: Benzalkonium chloride solution (50%) 0.26% w/w		
Batch No.:		Mfg. Lic. No.:
Sponsor: NovaLead Pharma Private Limited, Pune, INDIA		
Manufacturer:		
Store in cool environment		
Mfg. Date:		Exp. Date:
FOR CLINICAL TRIAL USE ONLY. NOT TO BE SOLD.		
FOR EXTERNAL USE ONLY		
Caution:		
Keep out of reach of children. In case of Emergency, contact your study doctor or Local Emergency Services		
Subject No.: To be written by study site		
Investigator's name: To be written by study site		
Investigator Contact Number: To be written by study site		
Name of the Institution: To be written by study site		
Visit No.: To be written by study site		
Date of dispensing: To be written by study site		
<hr/>		
Kit No.:		
Subject No.: To be written by study site		
Visit No.: To be written by study site		
Date of dispensing: To be written by study site		

The manufacturer will label the tubes, cartons and kits. In case additional IP is required for any Subject, new kit with same treatment will be issued.

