6.3 MEASURES TO MINIMIZE BIAS: RANDOMIZATION AND BLINDING

This is a double-blind study wherein the Investigator, the Sponsor, the Subject, the CRO and the Study Nurse Coordinator will be kept blinded to the randomization throughout the Study. There will be one unblinded Investigator per site who will administer the treatment during each treatment visit of the Subject as well as dispense the IP to the Study Nurse and the SoC material to the Subject. The Study Nurse who will administer treatment to the Subject (twice daily during Treatment Phase) will be unblinded. However, the unblinded Investigator and Study Nurse will still remain blinded to whether the Study drug applied is Galnobax® or Vehicle gel. The blinding of the Subject will be ensured by the Study Nurse by using shield while treating the Target Ulcer.

In case the Subject is staying far from the site (i.e. 40 km or more from the site) and/or Nurse is unable to visit every week to the site for treatment compliance check, following procedure will be followed for IP transport and compliance check: IP will be issued to the study Nurse at the time of the randomization visit along with study diary in an aluminum box having a lock. One key of this lock will be with the study Nurse and other with the unblinded CRC at the site. At the time of weekly site visit of the Subject, study Nurse will keep used IP tubes and Study diary in this box which will be locked and sent to the site with the Subject. Site unblinded CRC will take aluminum box from the subject and will check IP compliance as well as study diary. The IP will be reissued to the nurse after weighing the tubes and new study diary will also be issued (through which new dose of the subject will be conveyed to the Nurse). These materials will be kept in the aluminum box which will be locked and given to the Subject for handing over it to the study Nurse. This process will continue during all treatment visits.

While the IP compliance will be verified by the unblinded Investigator, the Target Ulcer Closure will be decided and confirmed by the blinded Investigator, thus mitigating any bias.

Unblinding will be done only if necessary for the welfare of the Subject or in the case of emergency suspected to be IP related. If such emergency is clearly not IP-related in the opinion of the Investigator, the Subject management can be done without the need of unblinding. Standard norms and procedures for unblinding will be followed.

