6.4 STUDY INTERVENTION COMPLIANCE

Blank Study diary will be dispensed to the Subject from Baseline Visit (V2). The Study Nurse will receive the blank diary from the Subject and record the daily compliance of the following during the Treatment Phase (V2-V14) as applicable:

- a. Off-loading
- b. Daily applications of the treatment (to confirm the dose application schedule),
- c. Missed applications,
- d. Excess dose drawing
- e. Completion of dressing of the Target Ulcer
- f. Any unusual happening

The Study Nurse will not disclose these entries to the Subject and retain the Study diary with her before submitting it to the unblinded Investigator. Collection and review of Study diary will

continue from V3 till V12 or EOT. The un-blinded Investigator will transcribe the information from the Study diary into the CRF. During the Treatment Phase, unblinded Investigator should record the weight of single application of treatment prescribed during every Treatment visit of the Subject and this basis will be used to check weekly compliance of the dose. The dose to be applied will be informed to the Study Nurse by the unblinded Investigator after every weekly Treatment visit. During Follow-Up Phase (V15-V18), Subject diary will be filled and handled by the Subject since there will be no treatment provided during the Follow-up. The Subject will hand over the completed Study Diary to the un-blinded Investigator during Follow-up visits.

The Subjects with treatment compliance of less than 80% or more than 120% of the IP, during the week, will be considered treatment non-compliant for that week. If such non-compliance is observed for more than three weeks, and if the blinded Investigator opines that it may affect the outcome of the Study, then the Subject shall be considered non-compliant for the Study and shall be discontinued from the Study.

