9.4 STATISTICAL ANALYSES

9.4.1 GENERAL APPROACH

Before database lock, a statistical analysis plan (SAP) will be issued as a separate document, providing the detailed methods for analyses outlined below. Any deviation from the planned analyses will be described and justified in the final integrated clinical Study report.

A maximum of 350 Subjects will be competitively recruited at 40 sites from the DFU Subject population as described in [section 4.1](#).

The number and percentage of all the DFU Subjects entering and completing the clinical Study will be provided across treatment groups. The summarization of primary reason of discontinuation will also be provided across treatment groups.

For this Study, analysis will be done on ITT Population (Safety Evaluable Population), FAS Population (Efficacy Evaluable Population) and PP Population.

The continuous data will be summarized by treatment Group using descriptive statistics (number of Subjects [n], Mean, Standard Deviation [SD], Median, Minimum and Maximum [Range]). Categorical data will be summarized by treatment group using frequency count (n) and percentages (%).

The primary and secondary efficacy analysis will be performed on all Subjects in FAS Population (Efficacy Evaluable Population) and PP Population comparing Group 1 (Galnobax® plus SoC) and Group 2 (SoC only). All the statistical analysis will be performed using SAS® version 9.4 or later.

The Safety analysis will be performed on all Subjects in ITT Population (Safety Evaluable Population).

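### Section 6.3 declares the Sponsor and CRO blinded, but gel returns, reconciliation and CRF items can identify every SoC-only subject while the SAP is still open

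*Combined protocol and SAP*

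**What the plan says.** Section 6.3 states that "the Investigator, the Sponsor, the Subject, the CRO and the Study Nurse Coordinator will be kept blinded to the randomization throughout the Study". It exempts one unblinded Investigator per site and the Study Nurse, and mentions an unblinded site coordinator. The unblinded Investigator and the nurse know gel from no gel but not Galnobax from Vehicle. Section 6.3 gives the compliance check to the unblinded Investigator and the closure decision to the blinded one.

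Other sections move gel-related material to the blinded parties:

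- Section 6.2.1: "Both used and unused IP tubes would be sent back to Sponsor/their representative for destruction as per standard procedure". It adds: "Reconciliation between the amount of IP supplied, used and returned to the Sponsor must be performed by the Sites and the CRO".
- Section 6.2.2: the label in Table 4 has a subject-number field, marked "To be written by study site". The section also says: "The manufacturer will label the tubes, cartons and kits".
- Section 6.4: the Study diary covers, where applicable, applications, missed applications, dressings and excess gel drawn. "The un-blinded Investigator will transcribe the information from the Study diary into the CRF". If gel use falls outside 80% to 120% in more than three weeks, the blinded Investigator judges whether this may affect the outcome. Section 7.2, item 6, repeats that judgement.

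On timing, section 9.4.1 says: "Before database lock, a statistical analysis plan (SAP) will be issued as a separate document". Sections 9.4.7 and 9.4.8 leave missing-data and outlier methods to that SAP. Section 9.4.6 plans no interim analysis, and section 9.4.10 gives the statistical evaluation to the CRO.

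**The concern.** Under section 6.1.2, SoC-only subjects receive saline and dressings but no gel. A returned tube, a reconciliation line or an excess-gel entry therefore marks a subject as a gel user, and having none of these marks the subject as SoC-only. Parties declared blinded are given tasks that reveal one whole side of the primary comparison, subject by subject, without any code being broken.

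At stake is the independence of choices still to be made. With 20% dropout planned, the missing-data rule matters. For example, the Definitions require closure to be confirmed at two further visits, while section 10.1.8 lists only missing both as a major deviation. How one missed confirmation visit counts in the primary endpoint is not stated. The major deviations that define the PP set are given as examples and rest on the Investigator's opinion. Rules of this kind should be fixed before anyone who writes them could tally closure by gel use.

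The second strand concerns the endpoint assessor. Section 6.4 expresses non-compliance as a percentage of the IP, which SoC-only subjects do not have. Asking the blinded Investigator to judge it tells that person that the subject is on gel.

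**Working it through.** **Plan's own figure.** Section 9.2 gives 39% against 60%, two-sided alpha 0.05, 90% power and 120 evaluable subjects per group. With the pooled-variance formula and a mean proportion of 0.495:

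n = [1.960 × √(2 × 0.495 × 0.505) + 1.2816 × √(0.39 × 0.61 + 0.60 × 0.40)]² / 0.21² = (1.386 + 0.886)² / 0.0441 ≈ 117.0, rounded up to 118.

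This agrees with 120 to within two subjects. Power at 120 per group is 90.7%, and 240 / 0.80 = 300. The design figures reproduce and are not in dispute.

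**Who can be identified.** Allocation is 3:3:1 (section 9.2.1). SoC-only is 3/7 of subjects, 150 of 350 at full recruitment. Gel users are 4/7, or 200. Among gel users the share on Galnobax is 3/(3 + 1) = 0.75, or 150 of 200.

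**What the visible contrast would show.** The Vehicle closure rate pV is not given, so it is an assumption here. The range runs from 24% (the global SoC average cited in section 9.2) to 60% (Vehicle as good as Galnobax).

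Visible difference = 0.75 × 0.60 + 0.25 × pV − 0.39.

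The power columns are for a two-sided 0.05 test of gel against SoC-only. They use 200 against 150 subjects, then 160 against 120 after 20% dropout.

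| Assumed pV | Gel users' rate | Visible difference (points) | Share of 21 points | Power, 200 v 150 | Power, 160 v 120 |
|---|---|---|---|---|---|
| 24% | 51.0% | 12.0 | 57% | 61% | 51% |
| 39% (equal to SoC) | 54.75% | 15.75 | 75% | 83% | 75% |
| 50% | 57.5% | 18.5 | 88% | 93% | 87% |
| 60% (equal to Galnobax) | 60.0% | 21.0 | 100% | 98% | 94% |

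The proxy is diluted unless Vehicle performs like Galnobax, but it is informative over most of this range.

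**Where the text is firm and where it is inferred.** The return to the Sponsor or its representative, the CRO's part in reconciliation, the labelling of tubes, the transcription of the diary and the blinded Investigator's judgement are all stated. That the subject number is on the tube itself is inferred: Table 4 is cited for the cartons, and the tube label is not shown separately. In the diary, all arms record twice-daily treatment, so only gel-specific items such as excess gel drawn reveal the arm.

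**The case against.** A reader might infer that the SAP's authors can see the primary contrast. The documents do not support this, for two reasons. The primary comparison is Group 1 against Group 2 only (section 9.4.2), while the records show Groups 1 and 3 together, and section 6.3 keeps Galnobax and Vehicle masked even from the unblinded Investigator and nurse. And no section names the SAP's authors or says that they receive tubes, logs or diary pages. The tubes may go to a representative, for destruction.

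The room for manoeuvre is also limited. Sections 9.3 and 9.4.2 already fix the endpoint, denominator, populations, logistic model and covariates. Outlier rules have little bearing on a yes/no endpoint. Linking the Sponsor's general right to end the study (section 10.1.2) to arm-level results would be speculation.

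On the CRF, silence about access settings is not evidence of open access, and no text says that the closure assessor opens the gel pages. A firewall could be described in section 10.1.4 (Key Roles and Study Governance), whose text was not available for this review.

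All of this stands and narrows the point. It does not remove the conflict between sections 6.3 and 6.2.1, the late SAP with its open missing-data rule, or the judgement that section 6.4 gives to the blinded Investigator. Section 10.1.5.2 adds to the conflict: CRO monitors review all site records holding original entries, which on its face includes the accountability log and the diary.

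**Conclusion.** The point holds in this form: the blind declared for the Sponsor and CRO does not extend to the SoC-only group. Every SoC-only subject, 3/7 of the trial, can in principle be identified from records that these parties are assigned to handle, while missing-data rules can remain open until just before database lock. The visible contrast is a proxy: 15.75 of the planned 21 points if Vehicle is assumed equal to SoC, and 12 to 21 points for Vehicle rates of 24% to 60%. Separately, sections 6.3 and 6.4 conflict over whether the closure assessor learns of gel compliance.

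This rests on three assumptions: that the subject number is completed on what is returned, that gel records and closure data can be linked by the same people, and that no firewall stands in section 10.1.4. The documents do not show that anyone has used or would use the information, and its effect on the trial result cannot be calculated from them. It should be corrected, but it does not invalidate the design.

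**What to change.** 1. Correct section 6.3 to say, role by role (Sponsor, CRO monitors, CRO statisticians, supply staff, site staff), who is masked to gel against no gel and who only to Galnobax against Vehicle. If a firewall exists, state it there.
2. Restrict eCRF pages with IP, tube-weight and gel-specific diary data to the unblinded site roles already planned. Keep return and reconciliation records away from anyone who handles outcome data or writes the SAP.
3. Finalise the SAP, including missing-data rules (with missed confirmation visits) and major-deviation rules, before subject-level gel records can be linked to closure data. The simplest date is before first randomisation.
4. Reconcile section 6.4, and item 6 of section 7.2, with section 6.3 so that the closure assessor does not receive IP-compliance information.

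The cost is earlier SAP work, eCRF access set-up and a short protocol amendment. Sample size, dosing and visits do not change. A separate unblinded supply or monitoring team would separate roles more fully but needs extra staff, and is not asked for here.
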